1.2. Schema

Figure 1: Schematic Overview of the Study

ETV: entecavir; NA: nucleos(t)ide analog; qd: once daily; TAF: tenofovir alafenamide; TDF: tenofovir disoproxil fumarate

NA: ETV, TDF, or TAF; qd dosing according to the prescribing information

All participants who complete 48-week study intervention should stop all study interventions including NAs at Week 48. After stopping all study interventions, participants will be monitored closely during the follow-up phase and should restart NA treatment in accordance with the NA re-treatment criteria (see Section '[NA Re-treatment Criteria and Monitoring After Stopping of NA](#)' for more details).

1.3. Schedule of Activities

Below are comprehensive schedules of activities that will be performed in this study, including those from the Master Protocol PLATFORMPAHPB2001. All differences with the Master Protocol PLATFORMPAHPB2001 (including the ISA-specific activities) are highlighted (colored fill).

1.3.1. Schedule of Activities – Screening and Study Intervention Phase

Phase	Screening	Double-blind Study Intervention ^a													
		W0 ^d	W2	W4	W8	W12	W16	W20	W24	W28	W32	W36	W40	W44	W48/WD ^b
Study Week (W)	W 4 to 0 ^c														
Study Day (Window)	28	1	15 (+/ 2d)	29 (+/ 2d)	57 (+/ 2d)	85 (+/ 2d)	113 (+/ 3d)	141 (+/ 3d)	169 (+/ 3d)	197 (+/ 3d)	225 (+/ 3d)	253 (+/ 3d)	281 (+/ 3d)	309 (+/ 3d)	337 (+/ 3d)
Screening/Administrative															
ICF ^e	X														
ICF for optional pharmacogenomic samples	X														
Inclusion/exclusion criteria ^f	X														
Prestudy therapy (including prior anti HBV therapy)	X														
Medical/surgical history and demographics ^g	X														
Preplanned surgery/procedure(s)	X														
Fibroscan or liver biopsy ^h	X														
Abdominal ultrasound ⁱ	X														
Serum IgM anti HBc antibody test	X														
Study Intervention															
Randomization to intervention arm within this ISA		X													
Administer JNJ 3989 (or placebo)		X		X	X	X	X	X	X	X	X	X	X	X	
Intake of JNJ 6379 (or placebo) and NA ^j		X	X	X	X	X	X	X	X	X	X	X	X	X	X
Dispense JNJ 6379 (or placebo) and NA		X		X	X	X	X	X	X	X	X	X	X	X	(X) ^k
Oral study intervention accountability			X	X	X	X	X	X	X	X	X	X	X	X	X
Safety Assessments															
Complete physical examination ^l	X									X					X
Symptom directed physical examination, including body weight		X	X	X	X	X	X	X		X	X	X	X	X	
Vital signs ^m	X	X	X	X	X	X	X	X	X	X	X	X	X	X	X
Triple 12 lead ECG ⁿ	X	X		X		X			X			X			X
Injection site reactions		X	X	X	X	X	X	X	X	X	X	X	X	X	X
Liver ultrasound ^o			X						X						X

Phase	Screening	Double-blind Study Intervention ^a													
		Study Week (W)	W 4 to 0 ^c	W0 ^d	W2	W4	W8	W12	W16	W20	W24	W28	W32	W36	W40
Study Day (Window)	28	1	15 (+/- 2d)	29 (+/- 2d)	57 (+/- 2d)	85 (+/- 2d)	113 (+/- 3d)	141 (+/- 3d)	169 (+/- 3d)	197 (+/- 3d)	225 (+/- 3d)	253 (+/- 3d)	281 (+/- 3d)	309 (+/- 3d)	337 (+/- 3d)
Clinical Laboratory Tests															
Hematology	X	X	X	X	X	X	X	X	X	X	X	X	X	X	X
Blood chemistry (including liver function tests) ^{p,q,r}	X	X	X	X	X	X	X	X	X	X	X	X	X	X	X
Blood coagulation	X	X		X	X	X	X	X	X	X	X	X	X	X	X
Urinalysis ^s	X	X		X	X	X	X	X	X	X	X	X	X	X	X
Urine chemistry ^t	X	X		X	X	X	X	X	X	X	X	X	X	X	X
Renal biomarkers ^u		X				X				X			X		X
Testing for hepatitis A, B, C, D, and E virus, HIV 1 and 2 ^r	X														
FSH test (postmenopausal women only) ^v	X														
Alpha fetoprotein ^r	X									X					X
Hemoglobin A1c test	X														
Serum pregnancy test (women of childbearing potential only)	X														
Urine pregnancy test (women of childbearing potential only)		X		X	X	X	X	X	X	X	X	X	X	X	X
Efficacy Assessments															
Fibroscan ^w			(X)												(X)
HBV Virology															
Blood sampling for HBV DNA	X	X	X	X	X	X	X	X	X	X	X	X	X	X	X
Blood sampling for HBV RNA ^x	X	X	X	X	X	X	X	X	X	X	X	X	X	X	X
Sampling for viral genome sequencing ^y	X	X		X		X			X		X		X		X
HBV Serology															
Blood sampling for:															
Anti HBs and anti Hbe	X	X								X					X
HBsAg and HBeAg (qualitative)	X	X								X					X
HBsAg (quantitative)	X	X	X	X	X	X	X	X	X	X	X	X	X	X	X
HBeAg (quantitative) ^z				X	X	X			X					X	X
HBcrAg ^x	X	X	X	X	X	X			X	X		X		X	X
Exploratory serology ^{aa}	X	X	X	X	X	X	X	X	X	X	X	X	X	X	X

Phase	Screening	Double-blind Study Intervention ^a													
		W 4 to 0 ^c	W0 ^d	W2	W4	W8	W12	W16	W20	W24	W28	W32	W36	W40	W44
Study Week (W)	W 4 to 0 ^c	15 (+/- 2d)	29 (+/- 2d)	57 (+/- 2d)	85 (+/- 2d)	113 (+/- 3d)	141 (+/- 3d)	169 (+/- 3d)	197 (+/- 3d)	225 (+/- 3d)	253 (+/- 3d)	281 (+/- 3d)	309 (+/- 3d)	337 (+/- 3d)	
Clinical Pharmacology Assessments															
Blood sampling for sparse PK of JNJ 3989, JNJ 6379, and/or NA ^{bb}		X ^{cc}		X ^{cc}		X ^{cc}			X ^{cc}						X ^{dd}
Blood sampling for intensive PK of JNJ 3989, JNJ 6379, and/or NA (PK subgroup) ^{ee}				X											
Exploratory Host Biomarkers															
Whole blood RNA gene expression		X				X			X						X
Whole blood single cell profiling		X		X	X	X			X			X			X
Host serum proteins (eg, cytokines)		X	X	X	X	X			X		X	X			X
Antidrug antibodies (to JNJ 3989)		X			X		X		X		X	X			
Immune Monitoring															
Immune cells (PBMCs) (selected sites only) ^{ff}		X							X						X
Pharmacogenomics (Host DNA)															
Exploratory host genotyping and epigenetic research (optional) ^{gg}		X							X						X
PRO Evaluations															
HBV specific self stigma scale	X	X							X						X
EQ 5D 5L		X							X						X
Ongoing Participant Review															
Concomitant therapy ^{hh}	X	X	X	X	X	X	X	X	X	X	X	X	X	X	X
Adverse events ^{hh}	X	X	X	X	X	X	X	X	X	X	X	X	X	X	X

General Note: The PRO assessments and ECGs should be completed before any tests, procedures or other consultations for that visit.

AFP: Alpha-fetoprotein; ALP: alkaline phosphatase; ALT: alanine aminotransferase; AST: aspartate aminotransferase; CKD-EPI: Chronic Kidney Disease Epidemiology Collaboration; CRF: case report form; CT: computed tomography; d: days; DBP: diastolic blood pressure; DNA: deoxyribonucleic acid; ECG: electrocardiogram; eGFR: estimated glomerular filtration rate; EQ-5D-5L: 5-Level EuroQol 5-Dimension; FSH: follicle-stimulating hormone; HBc: hepatitis B core protein; HBe(Ag): hepatitis B e (antigen); HBcrAg: hepatitis B core-related antigen; HBs(Ag): hepatitis B surface (antigen); HBV: hepatitis B virus; HCC hepatocellular carcinoma; HIV-1 (-2): human immunodeficiency virus type 1 (type 2); ICF: informed consent form; IgM: immunoglobulin M; ISA: intervention-specific appendix; MRI: magnetic resonance imaging; NA: nucleos(t)ide analog; PBMC: peripheral blood mononuclear cells; PK: pharmacokinetic; PRO: patient-reported outcome; RNA: ribonucleic acid; SBP: systolic blood pressure; ULN: upper limit of normal; W: Week; WD: withdrawal.

- All study visits are to be scheduled relative to the baseline (Day 1) visit date.
- Participants who discontinue study intervention early will have an early WD visit and will enter follow-up (see the follow-up Schedule of Activities in Section 1.3.2) unless they withdraw consent. Participants who withdraw consent will be offered an optional safety follow-up visit. For the optional safety follow-up visit, assessments are at the investigator's discretion and could be similar to the early WD visit.
- If necessary (eg, for operational reasons), the screening phase may be extended up to a maximum of 6 weeks in agreement with the sponsor.
- Day 1 samples are to be collected before the first dose of study intervention.

- e. Both the Platform Master ICF and the ISA ICF must be signed before the first study-related activity.
- f. Minimum criteria for the availability of documentation supporting the eligibility criteria are described in the Source Documents section in Attachment 3 of the Master Protocol PLATFORMPAHPB2001. Clinical status will be checked at screening and again before first dose of study intervention. If a participant's clinical status changes (including any available laboratory results or receipt of additional medical records) after screening but before the first dose of study intervention is given such that he or she no longer meets all eligibility criteria, then the participant should be excluded from participation in the study.
- g. Medical history also includes mode of HBV transmission, stage of liver fibrosis, and alcohol consumption. Historical HBV DNA, HBsAg, HBeAg, and ALT data, if available, will be recorded in the CRF and/or the source document. Available historical data on a previous HBV genotype assessment will also be collected in the CRF.
- h. Liver disease staging assessments will be performed based on Fibroscan or liver biopsy results, obtained within 6 months (in case of Fibroscan) or within 2 years (in case of liver biopsy) prior to screening or at the time of screening.
- i. Participants must have absence of signs of cirrhosis or portal hypertension (absence of nodules, smooth liver contour, normal portal vein, spleen size <12 cm) and absence of signs of HCC on an abdominal ultrasound performed within 6 months prior to screening or at the time of screening or clinically relevant renal abnormalities. In case of suspicious findings on conventional ultrasound the participant may still be eligible if HCC or clinically relevant renal abnormalities have been ruled out by a more specific imaging procedure (contrast enhanced ultrasound, CT or MRI).
- j. In between study visits, participants will take oral study intervention at home and they will bring their study intervention with them to each study visit. At study visits, the study intervention should be taken on site.
- k. NA will be dispensed at Week 48 for intake during the follow-up phase in case the participant cannot stop NA treatment at Week 48.
- l. Complete physical examination, including height (only at screening), body weight, skin examination, and other body systems.
- m. Vital signs include supine SBP, DBP, pulse rate, and body temperature.
- n. All ECGs will be read centrally. Only on Day 1, an ECG will be collected and assessed locally prior to dosing.
- o. A liver ultrasound is recommended every 6 months for HCC screening in high-risk populations (ie, participants with a family history of HCC, Asian males >40 years, Asian females >50 years; Africans and African Americans). The liver ultrasound does not need to be repeated at baseline if it was done within 6 months prior to screening or at the time of screening.
- p. Biochemistry samples must be taken after fasting for at least 10 hours for measurement of phosphate, calcium, creatinine, and lipids. If applicable, participants should bring their study intervention with them to each visit and have that day's intake at the site with breakfast.
- q. Creatinine clearance (eGFR calculated by the CKD-EPI formula) will be assessed.
- r. Intervention-emergent ALT/AST elevations (ie, ALT and/or AST ≥ 3 x ULN and ≥ 3 x nadir [ie, lowest value during study participation]), should trigger an assessment of confounding factors (alcohol intake, change in concomitant medication, and comorbidities) and a confirmatory visit, to be scheduled preferably within 7 days of the receipt of the initial ALT/AST results, to repeat laboratory testing of AFP, ALT, AST, ALP, bilirubin (total and direct), INR albumin, and HBV DNA. Additional tests should be considered based on clinical judgement. For more details and further management guidance, refer to Section 8.3.6.3, Intervention-emergent ALT/AST Elevations and Section 10.6, Appendix 6, Intervention-emergent ALT/AST Elevations.
- s. Urinalysis by dipstick: specific gravity, pH, glucose, protein, blood, ketones, bilirubin, urobilinogen, nitrite, leukocyte esterase, and microscopic analysis if needed. The dipstick reading should be done as soon as possible and in accordance with the manufacturer's recommendation. In case of a positive dipstick result, a urine sample will be set aside for additional examination of the positive parameter (eg, quantification as applicable).
- t. Urine chemistry sample (quantitative measurement): creatinine, sodium, phosphate, glucose, protein, and albumin.
- u. Urine sample for selected renal biomarkers including retinol binding protein and beta-2-microglobulin.
- v. For postmenopausal women only: an FSH level in the postmenopausal range may be used to confirm a postmenopausal state in women not using hormonal contraception or hormonal replacement therapy. However, in the absence of 12 months of amenorrhea, a single FSH measurement is insufficient to confirm a woman is not of childbearing potential (see Section 10.8 Appendix 8: Contraceptive and Barrier Guidance and Collection of Pregnancy Information).

- w. Only applicable to participants who are enrolled at a site with an on-site Fibroscan device. A Fibroscan assessment will only be done at baseline if it was not done at screening.
- x. HBcrAg and HBV RNA samples may be batched and only selected samples may be tested at the sponsor's request. Samples can be used for assessment of other serologic/virologic markers of HBV.
- y. Samples may be sequenced based on the sponsor virologist's request, considering the HBV DNA levels.
- z. Quantitative HBeAg assessment will only be performed in participants who become HBeAg-positive post baseline based on a qualitative HBeAg assay.
- aa. Exploratory serology samples may be analyzed at the sponsor's discretion. Samples may be used to assess virologic or serologic markers of HBV.
- bb. All participants will have sparse PK sampling. For all samples, the date and time of the preceding 2 intakes of oral study intervention (JNJ-6379/placebo and NA), the date and time of the previous JNJ-3989/placebo administration, and the date and time of PK sampling should be recorded. For participants in the intensive PK subgroup, the sparse PK sample does not need to be collected at the time of an intensive PK visit.
- cc. One sample at any time between 2 and 8 hours after JNJ-3989/placebo dosing. Before leaving the study site, the participant's wellbeing should be confirmed.
- dd. Only in case of early withdrawal.
- ee. All participants who consent to participate in the intensive PK subgroup (optional) will undergo intensive PK sampling at Week 4 (minimally 18 participants). If necessary (eg, for operational reasons), this visit may be scheduled at Week 8, 12, or 16. The study intervention should be taken on site and time of dosing should be recorded. Pharmacokinetic samples will be taken predose and 15 minutes, 30 minutes, 1, 2, 3, 4, 6, 8,* 10,* and 24 hours postdose (*the 8 and 10 hours postdose samples are optional). All efforts will be made to obtain the PK samples at the exact nominal time relative to dosing. However, samples obtained within 20% of the nominal time from dosing (eg, +/- 12 minutes of a 60-minute time point) will not be captured as a protocol deviation if the exact time of the sample collection is noted on the source document and data collection record (eg, CRF).
- ff. PBMC samples will be collected at selected sites only. Additional PBMC samples may be taken in case of ALT flares, upon discussion with the sponsor, and may require an unscheduled visit.
- gg. These samples are optional and will only be collected from participants who consent separately to this component of the study.
- hh. Adverse events and concomitant medications will be monitored from the time a signed and dated ISA ICF is obtained until completion of the participant's last ISA-related procedure.

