- a. All follow-up study visits are to be scheduled relative to the last dose of JNJ-3989/JNJ-6379/placebo. An unscheduled visit can be performed upon the investigator's discretion, in case of HBV DNA elevations, ALT elevations, other signs of worsening of liver disease, or for any other reason during follow-up.
- b. Participants who withdraw consent during follow-up will be offered an optional safety follow-up visit to occur on the day of consent withdrawal. For the optional safety follow-up visit, assessments are at the investigator's discretion and could be similar to the early WD visit.
- c. No JNJ-3989/JNJ-6379/placebo will be administered or dispensed during follow-up. Administration/Dispensation of NA is only applicable for participants who could not stop NA treatment at Week 48, or for those who met the NA re-treatment criteria. In between study visits, participants will take NA at home and they will bring their NA treatment with them to each study visit. At study visits, the NA treatment should be taken on site.
- d. Vital signs include supine SBP, DBP, pulse rate, and body temperature.
- e. All ECGs will be read centrally.
- f. A liver ultrasound is recommended every 6 months for HCC screening in high-risk populations (ie, participants with a family history of HCC, Asian males >40 years, Asian females >50 years; Africans and African Americans).
- g. Biochemistry samples must be taken after fasting for at least 10 hours for measurement of phosphate, calcium, creatinine, and lipids.
- h. Creatinine clearance (eGFR calculated by the CKD-EPI formula) will be assessed.
- i. ALT/AST elevations (ie, ALT and/or AST ≥ 3 ULN and ≥ 3 nadir [ie, lowest value during study participation]), should trigger an assessment of confounding factors (alcohol intake, change in concomitant medication, and comorbidities) and a confirmatory visit, to be scheduled preferably within 7 days of the receipt of the initial ALT/AST results, to repeat laboratory testing of AFP, ALT, AST, ALP, bilirubin (total and direct), INR albumin, and HBV DNA. Additional tests should be considered based on clinical judgement. For more details and further management guidance, refer to Section 8.3.6.3, Intervention-emergent ALT/AST Elevations and Section 10.6, Appendix 6, Intervention-emergent ALT/AST Elevations.
- j. Liver function tests only.

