An introduction on HBV and the current treatment options is provided in Section 2 of the Master Protocol PLATFORMPAHPB2001.

The term “study intervention” throughout the protocol, refers to JNJ-3989 or placebo for JNJ-3989, JNJ-6379 or placebo for JNJ-6379, and NA.

The term “sponsor” used throughout this document refers to the entities listed in the Contact Information page(s), which will be provided as a separate document.

The term “participant” throughout the protocol refers to the common term “subject”.

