6. STUDY INTERVENTION

6.1. Study Intervention(s) Administered

Description of Interventions

Intervention name	JNJ-3989	Placebo for JNJ-3989	JNJ-6379	Placebo for JNJ-6379	Entecavir (ETV) monohydrate	Tenofovir disoproxil fumarate (TDF)	Tenofovir alafenamide (TAF)***
Dosage formulation	Solution for injection	Solution for injection	Tablets	Tablets	Film-coated tablets	Film-coated tablets	Film-coated tablets
Unit dose strength(s)	200 mg/vial	0.9% saline	25 and 100 mg	-	0.5 mg	300 mg**	25 mg
Dosage regimen	200 mg once every 4 weeks	1 mL once every 4 weeks	250 mg qd	qd	Lamivudine-refractory patients: 1 mg* qd (but should preferably be treated with TDF or TAF instead) Other indications: 1 mg* qd (must be agreed upon by the sponsor)	300 mg qd	25 mg qd
Route of administration	Subcutaneous injection (in the abdomen)	Subcutaneous injection (in the abdomen)	Oral	Oral	Oral	Oral	Oral
Dosing instructions	Regardless of food intake	Regardless of food intake	Regardless of food intake	Regardless of food intake	On an empty stomach	With food	With food

qd: once daily

* 2 tablets of 0.5 mg

** 300 mg TDF is equivalent to tenofovir disoproxil 245 mg

*** In countries where TAF is available, it will be one of the NA treatment options.

Physical Description of Study Interventions

The JNJ-3989 supplied for this study will be provided as an aqueous clear, colorless to light yellow solution with 200 mg/mL of JNJ-3989 for subcutaneous injection [REDACTED]

[REDACTED].

The JNJ-6379 supplied for this study is formulated as oral tablets containing [REDACTED] mg ([REDACTED]) and [REDACTED] mg ([REDACTED]) JNJ-56136379-AAA. The JNJ-6379 tablets should be swallowed as a whole.

JNJ-3989 and JNJ-6379 will be provided under the responsibility of the sponsor. Refer to the iBs for a list of excipients.^{14,15,16}

The placebo for JNJ-3989 will be a solution for subcutaneous injection [REDACTED] [REDACTED]. The matching placebo for JNJ-6379 consists of the oral tablets without active drug substance [REDACTED] [placebo for [REDACTED] mg] and [REDACTED] [placebo for [REDACTED] mg]).

The NAs ETV, TDF, and TAF are formulated as oral film-coated tablets of 0.5-mg, 300-mg, and 25-mg strength, respectively.

Packaging and Labeling

All study interventions will be packaged with each unit labeled with a unique medication ID number. Packaging and labeling of JNJ-3989, the corresponding placebo, and the NAs will be done in an open-label way.

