Commercial supplies of NAs and sodium chloride will be sourced and a clinical study label will be applied.

Study intervention labels will contain information to meet the applicable regulatory requirements.

JNJ-6379 and matching placebo will be dispensed in child-resistant packaging. NA treatment may also be repackaged into child-resistant packaging if this is not already the case.

No study interventions can be repacked or relabeled without prior approval from the sponsor.

Study Intervention Administration

Study intervention administration must be captured in the source documents and the CRF.

JNJ-3989/placebo injections will be administered subcutaneously (preferably in the abdomen) at the study site.

In between study visits, participants will take their oral study intervention (JNJ-6379/placebo/NA treatment) at home and they will bring their oral study intervention with them to each study visit. At study visits, the oral study intervention should be taken on site to allow biochemistry and renal biomarker samples to be taken in fasted conditions.

NA treatment will be provided by the sponsor. Investigators should follow guidance detailed in the respective prescribing information, including special warnings and precaution for use.

During the study, participants will continue the same NA treatment they were receiving at time of screening (and during at least 3 months prior to screening). In case participants experienced toxicity to ETV, TDF, or TAF prior to screening, they should be treated with one of the other two NAs during this study.

If clinically indicated, switching from one NA treatment (ETV, TDF, or TAF) to another NA treatment (ETV, TDF, or TAF) during the study is allowed for all participants after consultation with the sponsor.

For a definition of study intervention overdose, refer to Section 8.4, Treatment of Overdose.

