8. STUDY ASSESSMENTS AND PROCEDURES

Overview

Refer to Section 8 of the Master Protocol PLATFORMPAHPB2001.

The PRO assessments and ECGs should be completed before any tests, procedures or other consultations for that visit.

The total blood volume to be collected from each participant during planned assessments for the entire study will be approximately 1200 mL. In addition, PBMC samples (at selected sites only; approximately 300 mL), optional exploratory host genotyping and epigenetic research samples (approximately 60 mL) and optional intensive PK samples (approximately 66 mL) may be collected.

Note: The total blood volume to be collected from each participant may vary, depending on several factors (eg, unscheduled re-tests, re-sampling, individual variations).

Sample Collection and Handling

Refer to Section 8 of the Master Protocol PLATFORMPAHPB2001.

Study-specific Materials

In addition to the items described in Section 8 of the Master Protocol PLATFORMPAHPB2001, the investigator will be provided with the following supplies:

- A binder with the PRO instruments,
- Prescribing Information for ETV, TDF, and TAF,
- Contact information page(s).

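### Schedule footnote p has visit-day study intervention taken with breakfast and does not exempt entecavir, which the dosing tables require on an empty stomach

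*Protocol*

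**What the plan says.** Footnote p is attached to the blood chemistry row of the schedule in Protocol Section 1.3.1. It requires a fast of at least 10 hours before sampling for phosphate, calcium, creatinine and lipids. It then says that participants should, if applicable, bring their study intervention to each visit and "have that day's intake at the site with breakfast". No agent is named and none is excepted. The Introduction says that the term study intervention "refers to JNJ-3989 or placebo for JNJ-3989, JNJ-6379 or placebo for JNJ-6379, and NA", and Appendix 1 lists the NA as entecavir, TDF or TAF.

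The table of interventions, printed in the Synopsis and again in Section 6.1, gives a food instruction for each agent. For entecavir it is "On an empty stomach". TDF and TAF are taken with food. JNJ-3989, JNJ-6379 and their placebos are given regardless of food.

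Three other places bear on NA dosing:

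- The Schema (Section 1.2) describes NA use as "qd dosing according to the prescribing information".
- Section 6.1 adds "Investigators should follow guidance detailed in the respective prescribing information".
- Section 8 lists "Prescribing Information for ETV, TDF, and TAF" among the materials given to sites.

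Footnote j of the same schedule says "At study visits, the study intervention should be taken on site" and does not mention food.

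**The concern.** A site reads the schedule of activities visit by visit, and footnote p is the instruction there that joins the dose to a meal. For an entecavir user it cannot be followed together with the dosing table. Entecavir users are an expected group, because type of NA (TDF/TAF versus entecavir) is one of the three randomization stratification factors.

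Two things are at stake. One is correct dosing of a background drug on visit days. The other is the interpretation of any entecavir concentrations, because the pharmacokinetic visits fall on those same days. Population pharmacokinetics of the NA is part of a secondary endpoint, as applicable.

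**Working it through.** The plan gives no figure to reproduce. The check compares the instructions and counts the visits they cover.

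**1. Footnote p against the dosing table, by oral agent**

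| Agent | Dosing table | Footnote p | Compatible? |
|---|---|---|---|
| JNJ-6379 or placebo | regardless of food | with breakfast | yes |
| TDF | with food | with breakfast | yes |
| TAF | with food | with breakfast | yes |
| Entecavir | empty stomach | with breakfast | no |

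JNJ-3989 is injected and has no food restriction. The conflict is confined to entecavir.

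**2. Is entecavir exempted anywhere?**

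- The if-applicable qualifier in footnote p names no drug. The blood chemistry row also covers screening, when there is no study drug to bring, and that is its most natural use.
- Footnote j and the administration text in Section 6.1 require on-site intake at visits. Section 6.1 gives the reason: biochemistry and renal biomarker samples are to be taken fasted. Neither separates entecavir from breakfast.
- The prescribing-information references in Sections 1.2, 6.1 and 8 point towards the empty-stomach rule. None mentions footnote p or sets an order of precedence.

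**3. Visits covered**

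Blood chemistry and on-site oral intake are both scheduled at Weeks 0, 2, 4, 8, 12, 16, 20, 24, 28, 32, 36, 40, 44 and 48, which is 14 visits. Study Days 1 to 337 give about 337 daily doses.

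- All visits: 14/337 = 4.2%.
- If Day 1, when drug is first dispensed and there is nothing to bring, is read as outside the footnote: 13/337 = 3.9%.
- With the 7 × 48 = 336 dosing days implied by SAP Section 4.7: 14/336 = 4.2%.

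**4. Overlap with pharmacokinetic sampling**

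The routine sparse samples are on Day 1 and at Weeks 4, 12 and 24. All 4 of these visits are on the list above (3 of 4 without Day 1). The intensive visit is Week 4, or Week 8, 12 or 16 if rescheduled, and each of these is also on the list.

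Two limits apply. Footnote cc times the sparse sample at 2 to 8 hours after the injection, so its position relative to the oral dose is not fixed. Footnote ee sets on-site dosing for the intensive visit without mentioning a meal, so breakfast reaches that visit only through footnote p.

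**5. Follow-up visits**

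The follow-up schedule (Section 1.3.2) repeats the fasting rule in footnote g: "Biochemistry samples must be taken after fasting for at least 10 hours for measurement of phosphate, calcium, creatinine, and lipids". Its footnote c has NA, where it is given, taken on site. Neither mentions breakfast, so the conflict does not extend to follow-up.

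**The case against.** The strongest reply is that a drug-specific dosing rule should prevail over a general note on a laboratory row. The entecavir instruction is printed twice, once in the section that governs dosing. Sites are told to follow the prescribing information and are supplied with it. A trained site would probably give entecavir fasted whatever footnote p says. That is a fair prediction of practice, and it is why the point is small. It does not make the footnote correct, because a site that follows it literally departs from the dosing table and no text says which governs.

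A second reply is that breakfast has a purpose, and this stands in full. Participants arrive after at least 10 hours without food and dose on site. Breakfast is what allows TDF and TAF users to take their dose with food. A reader might infer that the clause is superfluous and should be deleted, but the dosing table does not support that. The clause needs an exception for entecavir.

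A third reply is that the participant is already fasted at the draw, so the only question is the gap between the entecavir dose and the meal. This also stands. The protocol gives no interval defining an empty stomach. The prescribing information, the Master Protocol and the pharmacy or site procedures manual were not supplied, so the statement that nothing exempts entecavir is limited to the protocol and SAP.

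**Conclusion.** Footnote p is wrong as written for entecavir users and right for everyone else. Its reach is up to 14 visit-day doses per entecavir user (13 without Day 1), about 4% of intervention-phase doses, including the pharmacokinetic sampling days. These counts measure opportunity for misdosing. They do not show that it happens or what it does.

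A reader might infer that entecavir exposure, or the NA pharmacokinetic results, will be distorted. The documents do not support that. They give no food effect for entecavir, no carry-over from earlier home doses and no number of entecavir users. NA pharmacokinetic analysis is described as optional in Sections 8.5 and 9.4.3.

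A reader might also infer a risk to the efficacy comparison. Nothing in the documents gives a route to one. The primary endpoint is HBsAg seroclearance at Week 72 without NA restart, 24 weeks after all study interventions, including the NA, are due to stop. The footnote applies to both arms alike, and randomization is stratified by type of NA. Sample size, alpha and power are untouched.

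The point is minor: an internal inconsistency in a dosing instruction. Confidence is high in the conflict of wording. No claim is made about its effect on exposure. The conclusion assumes that study intervention in footnote p carries its defined meaning and that the if-applicable qualifier is not an unstated entecavir exception.

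**What to change.** Amend footnote p of Section 1.3.1 so that, after the fasting draw:

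- TDF or TAF is taken on site with breakfast;
- entecavir is taken on site on an empty stomach, separated from breakfast by the interval in its prescribing information.

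JNJ-6379 or its placebo can be taken at either time.

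The cost is one clause. Entecavir users wait for breakfast on up to 14 visit days. No visit, sample or analysis changes, and the follow-up schedule needs no edit.
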